The arguments in favor of virtual triage in the ED are much stronger. We expect that this change will reduce risk to patients, and risk to others, from violent outbursts. We expect that both phases will reduce patient discomfort, distress, and fear. Lessening decompensation by patients in the ED will allow therapeutic strategies to commence earlier, contributing to earlier recovery and earlier hospital discharge.

It is worth noting that our project is defensible on the basis of benefit to patients alone (otherwise, we would not consider it). There are other likely benefits, which do not enter directly into our calculus. This project is likely to reduce ED crowding. Also, this project will save the attending psychiatrist the need to travel to the hospital for most evaluations. We emphatically repeat that while these are indeed benefits, they are not the basis for us performing the study, nor would they be a sufficient reason for this change in policy.

2. Objectives

- i. We will implement tele-psychiatry evaluations in the ED.
- ii. We will evaluate the impact of this strategy on patient outcomes and healthcare utilization, compared to historical controls.

3. Working Hypotheses

- a. Remote video psychiatric examination is safe and effective, as measured by clinical outcomes, when compared to usual practice. Patients will spend fewer minutes in the ED, compared with historical controls. There will be fewer violent incidents in the ED. There will not be an increase in the frequency of reversal of involuntary hospitalization, which would imply that a patient was needlessly admitted.
- b. Implementation of telepsychiatry will be feasible within the current context, infrastructure, and resources.

4. Comprehensive description of study design and methodology:

Patient Population

We will recruit study participants from the Jerusalem Mental Health Center, located at Kfar Shaul and Ichilov Medical Center. We will obtain a waiver of informed consent, as this will be a change in standard procedure for all patients for the duration of the study.

We will include all patients who require an ED interview and an involuntary admission decision by a senior psychiatrist. We will compare patients from the three months prior to the study (approximately 60, based on usual rates of admissions) with patients from the three months of the study (also 60).

The absence of exclusion criteria will ensure that the study results will be broadly generalizable.

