Independent Variables (The Intervention)

In each study phase, the independent variable will be the study intervention, which will be organized by time. Patients in the pre-intervention period (3 months) will be managed under usual care, and will be the comparison group. Patients in the post-intervention period (3 months) will be managed using the study intervention, and will be the “intervention” group.

Usual care is that patients with psychiatric emergencies are evaluated face-to-face in the ED by a senior psychiatrist for possible involuntary admission. The intervention is that this evaluation will take place via video-link.

Dependent Variables

Dependent Variables

Variable	Type	Data Collection Method
Interobserver Variability	Binary	All video interviews will be recorded. A second senior psychiatrist, blinded to the admission decision, will determine whether admission was warranted based on the recording.
Reversal of Admission	Binary	An involuntary admission which is reversed within 24 hours implies an unnecessary admission. The proportion of admissions reversed within 24 hours will be measured.
Emergency Room Length of Stay	Continuous (minutes)	Measured from the time of arrival in the ED until the patient physically leaves the ED – to go home or to go to the psychiatry ward. Already collected as part of routine practice.
Time from ED arrival to assessment	Continuous (minutes)	We will measure this ourselves, starting with the pre-intervention period. We will measure time until the senior psychiatrist begins his/her face-to-face or virtual assessment.
Violent Incidents in the ED	Binary (any/none)	As recorded by ED staff and adjudicated by blinded review of the chart by a senior psychiatrist.
Patient satisfaction with ED course	Ordinal	We will ask patients to rate their overall satisfaction with their stay in the ED, from 1-5 (very dissatisfied – very satisfied), as they are leaving – starting with the pre-intervention period.
Staff satisfaction with ED flow	Ordinal	We will ask physicians, nurses, and other staff to rate their overall assessment of ED flow, from 1-5, at the end of each month
Duration of hospitalization	Continuous	From the time of entering the ward until the time of leaving the hospital, in hours

Statistical Analyses

We will be comparing the pre-intervention period with the post-intervention period. Above, we have outlined the dependent variables for each phase, and how we will collect them.

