We will start by comparing the pre- and post-groups on important baseline characteristics. These will include age, sex, ethnic/social group (Haredi, Arab, General Population), socioeconomic status, and underlying condition (schizophrenia, bipolar disorder, other). We will compare these variables between pre- and post-groups using appropriate bivariate tests (t-test, chi-square). If we find a statistically significant imbalance ($p < 0.05$), we will utilize a multivariable analysis in the main analysis to correct for the imbalanced factors. We do not propose to control for all potential covariates because of limited sample size.

In the main analysis, we will compare the dependent variables explained above between the pre- and post-periods. For continuous variables, we will use an unpaired t-test. For categorical variables, we will use a chi-square test. We will perform two-tailed tests, and will consider $p < 0.05$ to be statistically significant. In the event that we have detected an important between-group imbalance, we will use an appropriate regression model (logistic or generalized linear model), controlling for only the factors that have been found to be unbalanced.

Potential Sources of Bias

A sample size of 60 each in the pre- and post-intervention groups will make it unlikely, but not impossible, that random chance will lead to important between-group imbalance on measured factors. We will assess for such imbalance as part of the analysis plan, as noted above. If there are important differences, we will conduct multivariable analyses to control for a limited number of important unbalanced covariates.

Justification of Sample Size and Study Duration

The study duration is dictated by the maximal duration of a study funded by Machon HaLeumi. The sample size is dictated by the approximate number of patients admitted to our center each month. With 60 patients in the pre-intervention period and 60 in the post-intervention period, we will have statistical power to show a large effect size for some variables, and a moderate effect size for others. For example, if we assume that the average time in the ED is currently

3 ± 1 hours, and that the Phase 1 intervention will reduce this time by one hour, with 60 patients in each group, we would have 80% power to detect such a difference.

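### Reversal within 24 hours is measured only among admitted patients, so if video admits more of them, the measure understates the rise in reversed admissions per patient assessed

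*Combined protocol and SAP*

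**What the plan says.** Section 4, Dependent Variables, lists Reversal of Admission as a binary outcome. It gives the reason, "An involuntary admission which is reversed within 24 hours implies an unnecessary admission", and then the measure: "The proportion of admissions reversed within 24 hours will be measured". The denominator is involuntary admissions.

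The enrolled population is wider. Section 4, Patient Population, states: "We will include all patients who require an ED interview and an involuntary admission decision by a senior psychiatrist". Not all of these patients are admitted, because the same table times the emergency department (ED) stay "until the patient physically leaves the ED – to go home or to go to the psychiatry ward".

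Section 3, Working Hypotheses, states the safety expectation: "There will not be an increase in the frequency of reversal of involuntary hospitalization". It ties such an increase to needless admission but names no denominator.

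The proportion admitted does not appear in the Dependent Variables table. The blinded second opinion on whether admission was warranted is made from recordings of the video interviews. No recording of face-to-face interviews is described, so that item has no pre-period comparator.

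**The concern.** Whether a patient enters the denominator is decided by the assessment, and the assessment is what changes between the periods. The comparison is therefore made in a subset formed after the intervention has acted. If video shifts the threshold for admission, the two subsets are not the same kind of patient, and the per-admission proportion combines two effects: how many patients are admitted, and how often an admission is undone.

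Reversal is the only listed outcome that compares needless admission between the periods. If the proportion admitted rises, part of any increase in reversed admissions per patient assessed is absorbed by the larger denominator, and no other listed outcome would show it. The significance section says the results may inform Ministry of Health policy, so a reader will want to know whether more of the assessed patients ended up with an admission that was then undone.

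**Working it through.** The plan gives no admission rate, no reversal rate and no power figure for this outcome, so there is no figure of its own to reproduce. Its only power statement concerns time in the ED and plays no part here.

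**Identity (no assumptions).** For each period:

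reversed / admitted = (reversed / assessed) ÷ (admitted / assessed)

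Let f be the post-to-pre ratio of the proportion admitted. Then:

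ratio of the planned measure = ratio of reversals per patient assessed ÷ f

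**Direction.** Suppose A0 patients are admitted before, with reversal rate r0. Suppose video adds k admissions reversed at rate e, and the others are reversed as before. With the same number assessed, the planned measure after is (A0·r0 + k·e) / (A0 + k). This is below r0 if e < r0, equal to r0 if e = r0, and above r0 if e > r0. The count of reversals rises whenever e > 0.

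**Plausible size of f.** Section 1b reports agreement in 38 patients, each interviewed face-to-face and by video. Kappa for disposition and for the indication for involuntary admission ranged from 0.81 to 0.95 across the rater pairs. Treat admission as yes/no and let all disagreement run towards more admission by video. If face-to-face admits p and video admits q, observed agreement is at most 1 − (q − p), and chance agreement is pq + (1 − p)(1 − q). With p assumed to be 2/3, chance agreement is 1/3 + q/3, so the largest possible kappa is 1 − (q − 2/3)/(2/3 − q/3).

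- Kappa 0.81: q = (2/3 + 0.19 × 2/3)/(1 + 0.19/3) = 0.746, so f = 0.746/0.667 = 1.12.
- Kappa 0.95: q = (2/3 + 0.05 × 2/3)/(1 + 0.05/3) = 0.689, so f = 1.03.

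**Illustration near the upper of these values.** Assumed: 60 assessed in each period, and 40 admitted before with 4 reversed, which is 10.0% per admission and 6.7% per patient assessed. After: 45 admitted, so f = 45/40 = 1.125. The reversal counts below are expected values.

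| Reversal rate in the 5 added admissions | Reversed after | Per admission, after | Ratio | Per patient assessed, after | Ratio |
|---|---|---|---|---|---|
| 5% | 4.25 | 9.4% | 0.94 | 7.1% | 1.06 |
| 10% | 4.50 | 10.0% | 1.00 | 7.5% | 1.13 |
| 20% | 5.00 | 11.1% | 1.11 | 8.3% | 1.25 |

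In each row the per-admission ratio is the per-patient ratio divided by 1.125.

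**What 60 counts.** Patient Population gives the pre-period number as "approximately 60, based on usual rates of admissions", and Justification of Sample Size says "The sample size is dictated by the approximate number of patients admitted to our center each month". The inclusion rule, however, covers everyone needing a decision. If most of those assessed are admitted, f has little room: at an assumed 90% admitted it cannot exceed 1/0.90 = 1.11.

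**The case against.** The strongest reply is that the planned measure usually signals in the right direction. If video leads to extra admissions that are needless, those admissions should be reversed more often than the rest, and the per-admission proportion then rises. This stands. A reader might infer that the safety measure is likely to fall while needless admissions increase. The documents do not support that reading: a fall needs added admissions that are upheld more often than usual. What remains is that even a correct signal is smaller, in relative terms, than the change per patient assessed.

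A reader might also imagine a large shift, say from 40 to 52 of 60 admitted, which gives f = 1.30. That fits poorly with section 1b. Observed agreement could be at most 48/60 = 0.80 and chance agreement would be 0.622, so kappa could be at most (0.80 − 0.622)/(1 − 0.622) = 0.47, against the reported 0.81 to 0.95. With only 38 patients the earlier study does not exclude such a shift, but it points to something modest.

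Nor do the hypothesis and the outcome table contradict each other. The frequency of reversal can be read as reversals among hospitalizations, which matches the table, or as reversals among patients assessed.

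Two further points stand. The per-admission proportion answers a legitimate question, namely how often an admission is undone, and reversals per patient assessed also move with case mix. Events will be few under either definition: with 60 per period, power for 5% against 10% is about 18%, and for 10% against 20% about 33%. The plan itself accepts that some harm outcomes will not be definitive.

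**Conclusion.** The concern holds as an improvement to the measure. The per-admission proportion is computed in a subset selected by the assessment under study, and no listed outcome shows whether that subset grew. If the proportion admitted rises by a factor f, the planned measure understates the relative rise in reversed admissions per patient assessed by that factor.

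The size cannot be fixed from the documents. From an assumed 67% admitted, the earlier agreement data suggest f of about 1.03 to 1.12 even if all disagreement runs towards admission by video. This rests on 38 patients, on treating the decision as yes/no, and on agreement carrying over to practice. It is also unclear whether 60 counts patients assessed or admitted. The identity does not depend on that, but the room for f does.

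**What to change.** In the Dependent Variables table:

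- Add as a pre/post outcome the proportion involuntarily admitted among all eligible patients assessed.
- Define reversal for the main comparison as *involuntary admission reversed within 24 hours (yes/no) among all eligible patients assessed, with patients not admitted counted as no*.
- Keep the per-admission proportion beside it, and report the numbers assessed and admitted in each period.

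In Patient Population and Justification of Sample Size, say whether 60 counts patients assessed or patients admitted. In Working Hypotheses, name the denominator for the frequency of reversal.

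The cost is wording. Time to the senior psychiatrist's assessment is already to be recorded in both periods, so the patients assessed can be identified without new data collection. The drawbacks are that the per-patient percentage is smaller and also reflects case mix, which is why both versions should be shown with the proportion admitted. With few events, either version will be imprecise.

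### Monthly staff ratings of ED flow are repeated measures on an ordered scale, but the plan names only independent-sample tests for them, so the p-value for this outcome cannot be relied on

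*Combined protocol and SAP*

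**What the plan says.** In section 4 of the combined protocol and SAP, the Dependent Variables table lists staff satisfaction with ED flow as an ordinal outcome: "We will ask physicians, nurses, and other staff to rate their overall assessment of ED flow, from 1-5, at the end of each month". The lengths of the periods come from the text on independent variables: "Patients in the pre-intervention period (3 months) will be managed under usual care, and will be the comparison group", and "Patients in the post-intervention period (3 months) will be managed using the study intervention".

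Under Statistical Analyses the comparison covers every listed outcome: "In the main analysis, we will compare the dependent variables explained above between the pre- and post-periods". The tests are: "For continuous variables, we will use an unpaired t-test. For categorical variables, we will use a chi-square test". The threshold is two-sided 5%. The only alternative arises when baseline factors are imbalanced: "we will use an appropriate regression model (logistic or generalized linear model), controlling for only the factors that have been found to be unbalanced". That model has no term for the rater.

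The documents do not state how many staff rate, whether they are the same people before and after the switch, or whether forms are named, coded or anonymous. The rows for time to assessment and patient satisfaction say that collection begins in the pre-intervention period. The staff row does not, so pre-period ratings are only implied by the pre/post comparison.

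**The concern.** Ratings given by one person in successive months are correlated. If they are pooled and tested as separate observations, the standard error is wrong. With the same people in both periods, their personal tendencies cancel from the difference, the standard error is too large and the test is too cautious. With different people in each period, those tendencies do not cancel, the standard error is too small, and a change of raters can pass for an effect of video assessment.

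A second defect sits beside the first. The plan has no rule for ordinal outcomes. If a 1-5 rating is treated as categorical ("For categorical variables, we will use a chi-square test"), the ordering of the scale is thrown away.

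At stake is the p-value for one of eight listed outcomes. It is the only listed quantitative outcome that reflects how staff experience the change.

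**Working it through.** **No figure to reproduce.** The only power statement in the documents concerns patient ED time. Nothing is given for staff ratings, so the number of staff (20), the within-rater correlation ρ (0.3, 0.5, 0.7) and the overlap of staff between periods are all assumptions. From the documents come up to 3 ratings per person per period, the 1-5 scale, the named tests and the two-sided 5% level.

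**Step 1. Variance of the pre/post difference.** Take 3 ratings per person per period and let f be the share of staff who rate in both periods. The unpaired t-test takes the variance to be proportional to 2/3. The true value is proportional to 2(1-ρ)/3 + 2(1-f)ρ. So

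true variance / assumed variance = 1 + (2 - 3f)ρ, and

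actual type I error ≈ 2[1 - Φ(1.96/√ratio)].

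| Staff overlap | Ratio | ρ = 0.3 | ρ = 0.5 | ρ = 0.7 |
|---|---|---|---|---|
| All (f = 1) | 1 - ρ | 1.9% | 0.6% | 0.04% |
| Half (f = 0.5) | 1 + 0.5ρ | 6.8% | 8.0% | 9.2% |
| None (f = 0) | 1 + 2ρ | 12% | 17% | 21% |

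Example: f = 0, ρ = 0.5 gives a ratio of 2; 1.96/√2 = 1.386; two-sided tail 16.6%. The ratio equals 1 when f = 2/3, so the direction of the error turns at two-thirds overlap.

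**Step 2. Chi-square, by simulation.** A latent normal rating is cut at ±0.5 and ±1.5 into 1-5, with 20 staff and 3 ratings each per period. The type I error at ρ = 0.3 / 0.5 / 0.7 is:
- same staff: 3.5 / 2.6 / 1.4%
- half overlap: about 6 / 7 / 8%
- entirely different staff: 8 / 14 / 20%

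**Step 3. Where the power goes.** Same staff, 0.5 SD shift, same set-up:

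| Test | ρ = 0.3 | ρ = 0.5 | ρ = 0.7 |
|---|---|---|---|
| Chi-square on pooled ratings | 47% | 48% | 49% |
| Unpaired t on pooled ratings | 76% | 80% | 85% |
| Paired t on each person's means | 82% | 91% | 98% |

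Using the order of the scale recovers 76-47 = 29, 80-48 = 32 and 85-49 = 36 points. Pairing adds a further 6, 11 and 13.

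**Step 4. Shared month effects.** All staff rating in one month rate the same ED. With the same staff, no true effect, and a month effect of 5-10% of the variance (cut-points ±0.4 and ±1.2), the rejection rates across ρ = 0.3 to 0.7 are:
- chi-square: about 4-14%
- unpaired t: about 9-22%
- paired test on rater means: about 19-49%

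Pairing removes differences between raters, not differences between months. With three months on each side of the switch, it can make false positives more frequent.

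**The case against.** The strongest reply is that the documents do not settle the facts on which the size of the problem depends. Nowhere do they say that the same staff serve through both periods and act as their own controls. Two adjacent three-month periods make overlap plausible, but a fixed panel is not described, and the direction of the error turns on it. At about two-thirds overlap the unpaired t-test would even come close to its nominal level, by accident. All of this stands.

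Three further inferences are tempting and should not be drawn.
- A reader might conclude that a paired analysis will be impossible afterwards. The documents are silent on whether forms are identified, and silence does not show that ratings cannot be linked.
- A reader might conclude that failing to pair discards most of the information. With full overlap, the share of precision lost by not pairing equals ρ, so it is 30% at ρ = 0.3 and exceeds half only when ρ is above 0.5. The larger loss in step 3 comes from chi-square ignoring the ordering.
- A reader might regard a paired test as simply the correct one. Step 4 shows otherwise.

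It is also fair to say that staff satisfaction is not named in the working hypotheses, that the second objective concerns patient outcomes and utilization, and that the plan accepts that some outcomes will not be settled. An error here would not overturn the main conclusions.

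None of this makes the named tests suitable. They have no provision for repeated ratings by one person, and any agreement with 5% would be chance.

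**Conclusion.** The point holds in limited form. Repeated monthly ratings by staff are assigned to tests that require independent observations, and the resulting p-value is unreliable in a direction that the documents do not allow one to determine. Under the assumptions of 20 staff, three ratings each per period and ρ between 0.3 and 0.7, with no month effect, chi-square would reject falsely in about 1.4-3.5% of cases with the same staff throughout and 8-20% with entirely different staff. Confidence is high that the mismatch exists and low as to its exact size.

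The change should be made because it is cheap, and because pre-period ratings collected without a code may be hard to link later. The stake is one outcome of eight. Even a well-chosen rater-level analysis yields supportive evidence only.

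**What to change.** - State that staff ratings start in the first pre-intervention month, and put an anonymous rater code on the form from then on.
- For this outcome, replace the unpaired t-test or chi-square with a rater-level analysis that uses the order of the scale. This can be a paired comparison of each person's pre and post means, or an ordinal or linear mixed model with a rater effect, which keeps partial responders.
- Report how many staff rated in both periods and how many in only one.
- Show the mean rating for each month, say that three months per period cannot separate shared month effects from the intervention, and label the result supportive.

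The cost is a code on the monthly form and a few sentences in Statistical Analyses. A coded form is slightly less anonymous, and staff who rated in only one period add little to the paired estimate.

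### The before-after comparison adjusts only for baseline factors that differ at p<0.05; a covariate set fixed in advance for the continuous outcomes would be a cheap improvement, with a gain that depends on how well the factors predict outcome

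*Combined protocol and SAP*

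**What the plan says.** The groups are defined by calendar period, as section 4 (Independent Variables) states: "In each study phase, the independent variable will be the study intervention, which will be organized by time". Three months of usual care are compared with three months of the intervention, about 60 patients in each.

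Section 4, Statistical Analyses, lists five baseline factors: age, sex, "ethnic/social group (Haredi, Arab, General Population), socioeconomic status, and underlying condition (schizophrenia, bipolar disorder, other"). Each is tested between periods, with this rule: "If we find a statistically significant imbalance ($p < 0.05$), we will utilize a multivariable analysis in the main analysis". The regression is then fitted "controlling for only the factors that have been found to be unbalanced". Otherwise the main analysis is an unpaired t-test or a chi-square test. The reason given is: "We do not propose to control for all potential covariates because of limited sample size".

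Potential Sources of Bias treats imbalance as a matter of chance, saying that 60 per group "will make it unlikely, but not impossible, that random chance will lead to important between-group imbalance on measured factors". No section provides an adjusted analysis that is always carried out.

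**The concern.** Nothing in the design balances consecutive calendar periods, so case-mix can differ systematically as well as by chance. The bias from an unadjusted factor depends on the size of its imbalance and on its link with outcome. A baseline p-value measures neither: it mixes the size of the difference with the sample size and ignores prognosis. A moderate imbalance in a strong predictor can pass unadjusted, while a chance difference in an irrelevant factor triggers a model.

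The sample-size reason is sound for sparse binary outcomes such as violent incidents or reversal within 24 hours. It is weak for ED length of stay and time to assessment, where the five factors need about 7 parameters for about 120 patients. At stake are some residual bias from measured case-mix and some lost precision.

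**Working it through.** **Inputs from the plan.** 60 per period; two-sided 0.05; five factors, two of them with three levels; a power example with ED time of 3 ± 1 hours and a 1-hour reduction.

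**Assumptions.** The share of outcome variance explained by the five factors (R²) is not in the documents and is varied from 0 to 30%. Socioeconomic status is taken as one term, giving k = 7 parameters.

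**The plan's own power figure.** Reading ± 1 hour as an SD, 60 per group and a 1-hour difference give 99.97% power (noncentral t), not the stated 80%; about 17 per group would give 80%. That discrepancy is a separate matter. Here it means that the 1-hour effect is detected with or without adjustment: simulated power at a 1 SD effect is at least 99.8% under either approach.

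**What the screen can see.** A continuous factor is flagged when the observed difference exceeds t(0.975, 118) × √(2/60) = 1.980 × 0.1826 = 0.362 SD.

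| True imbalance | Flagged | Missed |
|---|---|---|
| 0.2 SD | 19% | 81% |
| 0.3 SD | 37% | 63% |
| 0.4 SD | 58% | 42% |
| 0.5 SD | 78% | 22% |

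For sex, the smallest gap flagged is 11/60 = 18 percentage points (uncorrected chi-square; 12/60 = 20 points with continuity correction). Three-level factors have no single cutoff; as an example, 40/30/30% against 55/22.5/22.5% is flagged 29% of the time. With no true imbalance and five independent factors, 1 − 0.95⁵ = 23% of studies would still flag at least one.

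**Bias left by the rule.** Simulation with no true effect, 60 per period, each factor carrying R²/5, shifts of 0.2 SD and outcome SD about 1:

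| R² | One factor shifted | Five shifted, mean over 16 sign patterns (false-positive rate) | Five shifted, same direction (false-positive rate) |
|---|---|---|---|
| 5% | 0.010 SD | 0.022 SD (5.1%) | 0.061 SD (5.8%) |
| 10% | 0.016 | 0.033 (5.4%) | 0.088 (7.6%) |
| 20% | 0.019 | 0.045 (5.6%) | 0.121 (9.2%) |
| 30% | 0.025 | 0.055 (5.7%) | 0.151 (12.6%) |

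A second run of the last column gave 0.080, 0.114 and 0.141 SD at 10, 20 and 30%. With four factors shifted in cancelling directions the bias is under 0.01 SD. Fixed adjustment leaves at most 0.004 SD, with a false-positive rate of 4.5-5.6%.

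Hand check of the last column: with no adjustment the bias is 5 × 0.2 × √(R²/5) = √(R²/5), or 0.10, 0.14, 0.20 and 0.24 SD. The rule therefore leaves roughly three-fifths of it. If 1 hour is the SD of ED time, 0.15 SD is 0.15 × 60 = 9 minutes.

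**Precision.** The variance of the adjusted period effect relative to the t-test is (1 − R²) × [1 + k/(N − k − 3)]. With N = 120 and k = 7 the bracket is 1 + 7/110 = 1.064, so break-even is R² = 1 − 1/1.064 = 6%. With k = 9 (socioeconomic status in four levels) it is 1 + 9/108 = 1.083, and break-even is about 8%.

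Simulated power at a 0.5 SD effect with no imbalance, plan / fixed adjustment:

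| R² | 60 per period | 40 per period (assumed) |
|---|---|---|
| 0% | 77.0 / 75.2 | 58.3 / 55.8 |
| 5% | 76.6 / 76.7 | 58.7 / 57.8 |
| 10% | 77.0 / 78.9 | 59.8 / 61.0 |
| 20% | 77.6 / 83.7 | 60.1 / 65.4 |
| 30% | 78.6 / 88.0 | 59.4 / 71.0 |

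Monte Carlo error is about 0.5 point. The 40-per-period column stands for duration of hospitalization, which runs "From the time of entering the ward until the time of leaving the hospital, in hours". An ED stay may also end with the patient leaving "to go home or to go to the psychiatry ward", so fewer than 60 per period may contribute.

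**The case against.** The strongest case against is that typical harm is small and the remedy may gain little where the plan is most specific. Averaged over sign patterns the bias is 0.02-0.06 SD, about 1-4 minutes of ED time on a 1-hour SD, and the false-positive rate stays near 5%. The worst case needs all five factors to line up, which is 1 of 16 patterns if signs are independent, though correlated case-mix shifts could make it commoner. Section 1 attributes the ED wait to the senior psychiatrist being away from the hospital, so patient factors may explain little of ED time. Below about 6-8% of variance explained, fixed adjustment gains no precision. All of this stands, and it limits the point to an improvement.

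The plan also speaks of important differences, which could leave room for judgement beyond the p-value. But importance is not defined, and the only explicit trigger is p<0.05.

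Underlying condition needs care. The documents do not say whether it comes from prior records or from the assessment that the intervention replaces. In the latter case it is not clearly a baseline factor. This objection stands and is met in the fix.

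A reader might infer that the screen invalidates the main result or seriously inflates false positives. The documents do not support that: they give neither shifts nor associations, and inflation appears only in the aligned scenario.

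**Conclusion.** The point holds as a cheap improvement to the analysis, not as a fatal flaw. The miss rates of 81% and 63% at 0.2 and 0.3 SD follow from the plan's own sample size and threshold. The consequences rest on assumed shifts and assumed R²: usually 0.01-0.06 SD of bias, and 0.06-0.15 SD only when all five factors move in the same outcome-relevant direction. The likelier benefit is precision for effects smaller than the planned 1 hour, provided the factors explain about 10% or more of outcome variance.

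It would be wrong to infer that fixed adjustment repairs the before-after design. It does nothing about calendar trends, unmeasured differences or selection into admission.

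**What to change.** - **Main analysis.** Delete the p<0.05 screen. For ED length of stay, time to assessment and duration of hospitalization, make the main analysis a regression on period that includes age, sex, ethnic/social group, socioeconomic status and underlying condition. Show the unadjusted t-test beside it, report baseline differences as standardised differences, and state the scale of socioeconomic status.
- **Underlying condition.** Take it from the record before the senior psychiatrist's assessment. If it is available only from that assessment, leave it out of the main model and show it as a sensitivity analysis.
- **Other outcomes.** For patient satisfaction and the sparse binary outcomes, name one small covariate set now, on prognostic grounds.
- **Duration of hospitalization.** Choose the full or the small set now, not after seeing how many patients were admitted.
- **Missing covariates.** Keep these patients in the model, by a missing category or by single imputation with an indicator.
- **Limits.** State that calendar-time differences, unmeasured differences and selection into admission remain.

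The cost is analysis wording, a missing-data rule and settling the source of underlying condition; all five factors are already to be compared at baseline. If they predict nothing, power at a 0.5 SD effect falls about 2 points (2-3 with 40 per period). The missing-data rule matters: with socioeconomic status missing in 10% and R² = 10%, fixed adjustment has 74.8% power on complete cases and 79.0% with imputation plus an indicator, against 77.0% for the plan's rule with complete data.
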